### **3. INTRODUCTION**

This SAP has been developed after review of the Clinical Study Protocol (final version dated 30 September 2020).

This SAP describes the planned analysis of the safety, tolerability, and pharmacokinetic (PK) data from this study. A detailed description of the planned TFLs to be presented in the clinical study report (CSR) is provided in the accompanying TFL shell document.

The intent of this document is to provide guidance for the statistical and PK analyses of data. In general, the analyses are based on information from the protocol, unless they have been modified by agreement with Eli Lilly and Company. A limited amount of information concerning this study (e.g., objectives, study design) is given to help the reader's interpretation. When the SAP and TFL shells are agreed upon and finalized, they will serve as the template for this study's CSR.

This SAP supersedes the statistical considerations identified in the protocol; where considerations are substantially different, they will be so identified. If additional analyses are required to supplement the planned analyses described in this SAP, they may be performed and will be identified in the CSR. Any substantial deviations from this SAP will be agreed upon with Eli Lilly and Company and identified in the CSR. Any minor deviations from the TFLs may not be documented in the CSR.

This SAP is written with consideration of the recommendations outlined in the International Conference on Harmonisation (ICH) E9 Guideline entitled Guidance for Industry: Statistical Principles for Clinical Trials and the ICH E3 Guideline entitled Guidance for Industry: Structure and Content of Clinical Study Reports.

### **4. STUDY OBJECTIVES**

#### **4.1 Primary Objective**

The primary objective of the study is to determine the PK of single subcutaneous (SC) doses of LY3832479 in healthy participants.

The primary endpoints of the study are the area under the concentration versus time curve from time zero to infinity (AUC [0-∞]) and the maximum observed drug concentration (Cmax).

#### **4.2 Secondary Objective**

The secondary objective of the study is to describe safety and tolerability following single SC doses of LY3832479 in healthy participants.

The secondary endpoints of the study are:

- Incidence of spontaneously reported adverse events (AEs), treatment-emergent adverse events (TEAEs), and serious adverse events (SAEs)

- vital signs
- clinical laboratory results.

#### 4.3 Exploratory Objectives

The exploratory objectives and endpoints of the study are:

- To assess injection site reactions (ISRs) following single SC doses of LY3832479 in healthy participants
  - Characterization and measurement of incidence and severity of ISRs (including injection site pain) using data collected from the ISR assessment, as well as the exploratory tool (Scarletred)
- To determine the immunogenicity of LY3832479 following single SC doses in healthy participants.
  - Incidence of treatment-emergent antidrug antibodies (TEADA)

### 5. STUDY DESIGN

This is a single-site study in healthy participants who will receive a single SC dose of LY3832479. The study will be participant- and investigator-blinded, randomized, and placebo controlled.

Up to 2 cohorts may be enrolled with at least 9 participants per cohort (7 LY3832479 : 2 placebo), with the intention that at least 6 participants randomized to LY3832479 have sufficient evaluable data in each cohort.

Participants will be screened within 14 days prior to Day 1 of dosing for each cohort. Participants will be admitted to the clinical research unit (CRU) as part of an inpatient visit on Day -1 and will be sequentially enrolled and then randomized to treatment.

Participants will be admitted to the study site on Day -1. They will remain inpatient until discharge on Day 7 after study procedures are complete.

Dosing will occur on Day 1. Intended doses of LY3832479 are as follows:

[figure not shown]
- Cohort 1: 350 mg
- Cohort 2: 1000 mg

Participants will undergo PK sampling and safety assessment after dosing.

For Cohort 1, a safety review will be conducted to determine whether it is appropriate to proceed with dosing of the next cohort. This safety review will be conducted based on data from at least 5 participants, after at least 4 days after dosing.

On Days 1 through 7, participants will undergo PK sampling and safety assessment.

A general schema for this study can be seen in [Figure 1](#).

Abbreviations: LY = LY3832479; PBO = placebo.

**Figure 1 – General schema for PGAB**

## 6. TREATMENTS

The following is a list of the study treatment abbreviations that will be used in the TFLs.

Cohort	Study Treatment Name	Treatment order in TFL
All	Placebo SC	1
1	350 mg LY3832479 SC	2
2	1000 mg LY3832479 SC	3

## 7. SAMPLE SIZE JUSTIFICATION

A maximum of 22 participants will be enrolled to study intervention with the intention that at least 6 participants randomized to LY3832479 have sufficient evaluable data in each cohort.

The sample size is not powered on the basis of statistical hypothesis testing. However, based on an assumption of 40% coefficient of variation (CV%) for between subject variability in a PK parameter of interest, 6 participants on active treatment per cohort may provide approximately 70% chance to ensure that a PK parameter's 90% confidence interval (CI) falls within (0.7, 1.43) over the corresponding geometric mean, such as AUC (0- $\infty$ ).

## 8. DEFINITION OF ANALYSIS POPULATIONS

The “Entered” population will consist of all participants who signed the informed consent form (ICF).

The “Enrolled / Intent-to-Treat” population will consist of all participants assigned to treatment, regardless of whether they received study treatment, or if they took the correct treatment. Participants will be analyzed according to the treatment group to which they were assigned.

The “Safety” population will consist of all participants randomly assigned to study intervention and who received study intervention. Participants will be analyzed according to the intervention they actually received.

The “Pharmacokinetic” population will consist of all treated participants who received a full dose of study intervention and have sufficient evaluable PK samples. Participants who did not receive a full dose (fewer injections than planned) would still have their PK analyzed, but the results will be reported separately and not included in the main analyses.

All protocol deviations that occur during the study will be considered for their severity/impact and will be taken into consideration when participants are assigned to analysis populations.

## **9. STATISTICAL METHODOLOGY**

### **9.1 General**

Data listings will be provided for all data that is databased. Summary statistics and statistical analysis will only be presented for data where detailed in this SAP. For continuous data, summary statistics will include the arithmetic mean, arithmetic standard deviation (SD), median, min, max and N; for log-normal data (e.g. the PK parameters: AUCs and  $C_{max}$ ) the geometric mean and geometric CV% will also be presented. For categorical data, frequency count and percentages will be presented. Data listings will be provided for all participants up to the point of withdrawal, with any participants excluded from the relevant population highlighted. Summary statistics and statistical analyses will generally only be performed for participants included in the relevant analysis population. For the calculation of summary statistics and statistical analysis, unrounded data will be used.

Mean change from baseline is the mean of all individual participants' change from baseline values. Each individual change from baseline will be calculated by subtracting the individual participant's baseline value from the value at the timepoint. The individual participant's change from baseline values will be used to calculate the mean change from baseline using a SAS procedure such as Proc Univariate.

Data analysis will be performed using SAS® Version 9.4 or greater.

### **9.2 Demographics and Participant Disposition**

Participant disposition will be summarized and listed. The demographic variables age, sex, race, ethnicity, body weight, height and body mass index will be summarized and listed. All other demographic variables will be listed only.

### **9.3 Pharmacokinetic Assessment**

#### **9.3.1 Pharmacokinetic Analysis**

Noncompartmental methods applied with a validated software program, Phoenix WinNonlin (Certara, Version 8.1 or later) to the serum concentrations of LY3832479 will be used to determine the following PK parameters, when possible:

Parameter	Units a	Definition
AUC(0-∞)	µg*day/mL	Area under the concentration versus time curve from time zero to infinity
%AUC(t last -∞)	%	Percentage of AUC(0-∞) extrapolated
AUC(0-t last )	µg*day/mL	Area under the concentration versus time curve from time zero to time t, where t is the last time point with a measurable concentration
C max	µg/mL	Maximum observed drug concentration
t ½	day	Half-life associated with the terminal rate constant ( $\lambda_z$ ) in non-compartmental analysis
t last	day	Time of the last observed drug concentration
t max	day	Time of maximum observed drug concentration
CL/F	L/day	Apparent total body clearance of drug calculated after extra-vascular administration
V z /F	L	Apparent volume of distribution during the terminal phase after extra-vascular administration
V ss /F	L	Apparent volume of distribution at steady state after extra-vascular administration

a Units of source LY3832479 serum concentration data will be ng/mL, to one decimal place.

Additional PK parameters may be calculated, as appropriate. The software and version used for the final analyses will be specified in the clinical study report. Any exceptions or special handling of data will be clearly documented within the final study report.

Formatting of tables, figures and abbreviations will follow the Eli Lilly Global PK/PD/TS Tool: NON-COMPARTMENTAL PHARMACOKINETIC STYLE GUIDE. The version of the tool effective at the time of PK analysis will be followed.

### General PK Parameter Rules

- Actual sampling times will be used in the final analyses of individual PK parameters, except for non-bolus pre-dose sampling times which will be set to zero.
- Cmax and tmax will be reported from observed values. When reporting unit-transformed individual Cmax values (and the corresponding minimum, median, and maximum values) the original significance will be maintained (eg 12345.6 ng/mL becomes 123.456 µg/mL; other summary statistics will be rounded to 3 significant digits). If Cmax occurs at more than one time point, tmax will be assigned to the first occurrence of Cmax.
- AUC parameters will be calculated using a combination of the linear and logarithmic trapezoidal methods (linear-log trapezoidal rule). The linear trapezoidal method will be applied up to tmax and then the logarithmic trapezoidal method will be used after tmax. The minimum requirement for the calculation of AUC will be the inclusion of at least three consecutive serum concentrations above the lower limit of quantification (LLOQ), with at least one of these concentrations following Cmax. AUC(0-∞) values where the percentage

of the total area extrapolated is more than 20% will be flagged. Any  $AUC(0-\infty)$  value excluded from summary statistics will be noted in the footnote of the summary table.

- Half-life ( $t_{1/2}$ ) will be calculated, when appropriate, based on the apparent terminal log-linear portion of the concentration-time curve. The start of the terminal elimination phase for each participant will be defined by visual inspection and generally will be the first point at which there is no systematic deviation from the log-linear decline in serum concentrations. Half-life will only be calculated when a reliable estimate for this parameter can be obtained comprising of at least 3 data points. If  $t_{1/2}$  is estimated over a time window of less than 2 half-lives, the values will be flagged in the data listings. Any  $t_{1/2}$  value excluded from summary statistics will be documented in the footnote of the summary table.
- A uniform weighting scheme will be used in the regression analysis of the terminal log-linear portion of the concentration-time curve.
- The parameters based on predicted  $C_{last}$  will be reported.

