## **13. DATA PRESENTATION**

### **13.1 Derived Parameters**

Individual derived parameters (e.g. PK parameters) and appropriate summary statistics will be reported to three significant figures. Observed concentration data, e.g.  $C_{max}$ , should be reported as received. Observed time data, e.g.  $t_{max}$ , should be reported as received. N and percentage values should be reported as whole numbers. Median values should be treated as an observed parameter and reported to the same number of decimal places as minimum and maximum values.

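### Does the misplaced decimal point in the SAP's ng/mL-to-µg/mL example put the reported Cmax at risk?

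*SAP*

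**What the plan says.** SAP Section 4.1 names AUC(0-∞) and Cmax as the primary endpoints.

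The parameter table in SAP Section 9.3.1 gives the reporting unit for Cmax ("µg/mL Maximum observed drug concentration"), and its footnote gives the unit of the incoming data: "Units of source LY3832479 serum concentration data will be ng/mL, to one decimal place".

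The General PK Parameter Rules in the same section then deal with precision. For unit-transformed individual Cmax values "and the corresponding minimum, median, and maximum values", "the original significance will be maintained (eg 12345.6 ng/mL becomes 123.456" µg/mL. The remaining summary statistics are to be rounded to three significant digits.

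SAP Section 13.1 adds that derived parameters go to three significant figures, whereas observed concentrations, with Cmax as the example, "should be reported as received".

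**The concern.** The example is the only worked ng/mL-to-µg/mL conversion in the SAP, and it is wrong. The factor of 1000 is not written out anywhere. The example also sits inside an operative rule that covers the individual values, minimum, median and maximum of a primary endpoint.

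The trial plans no hypothesis test (Protocol Section 9.1), so the descriptive PK summary is the result. SAP Section 3 makes the SAP and its table shells the template for the study report. A programmer who took the divisor from the example would report Cmax tenfold too high. A checker who compared correct output with the example would see a false mismatch.

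**Working it through.** **Inputs**

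- Source unit: ng/mL, one decimal place (SAP 9.3.1, table footnote).
- Reporting unit for Cmax: µg/mL (SAP 9.3.1, table).
- Example: 12345.6 ng/mL shown as 123.456 µg/mL (SAP 9.3.1, General PK Parameter Rules).
- Assumed between-subject CV: 40% (SAP Section 7; Protocol Section 9.2).

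**1. The conversion.** 1 µg = 1000 ng and the volume unit is unchanged, so value in µg/mL = value in ng/mL ÷ 1000.

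- 12345.6 ÷ 1000 = 12.3456 µg/mL.
- Printed value ÷ correct value = 123.456 ÷ 12.3456 = 10.
- Divisor implied by the example = 12345.6 ÷ 123.456 = 100.

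The printed figure cannot be reproduced. Other target units do not rescue it: mg/L and ng/µL give 12.3456, µg/L gives 12345.6, µg/dL gives 1234.56 and mg/dL gives 1.23456. For 123.456 µg/mL to be right, the source value would have to be 123456.0 ng/mL. The documents do not show which of the two numbers was mistyped.

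**2. What the example is for.** The rule concerns significance. 12345.6, 123.456 and 12.3456 all carry six significant digits. The contrast is with rounding to three digits, which would turn 12.3456 into 12.3. On that point the example does its job whichever way the decimal point is repaired.

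**3. What decides the factor.** The two unit labels in Section 9.3.1 decide it, and they leave no choice. The example carries the same labels, so anyone reading 100 out of it must contradict the labels printed beside the numbers.

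**4. Would a tenfold slip stay hidden?** There are two cases.

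- *Only the values named in the rule are inflated (individual, minimum, median, maximum), and the means are correct.* The printed minimum would then exceed the correct geometric mean unless some participant's true Cmax lay below one tenth of that mean. With a 40% CV and log-normal data, the log-scale SD is √ln(1 + 0.40²) = √ln(1.16) = 0.385. One tenth of the geometric mean is ln(10) ÷ 0.385 = 2.303 ÷ 0.385 ≈ 6.0 SDs below it. A minimum above the mean would almost certainly be printed, and it is an obvious impossibility.
- *Every Cmax statistic is inflated.* The Cmax summary would then agree with itself. However, SAP Section 9.1 requires listings of all databased data, so each Cmax could be compared with that participant's source concentrations in ng/mL.

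**5. Effect on comparisons.** A constant factor cancels between cohorts: (10 × Cmax at 1000 mg) ÷ (10 × Cmax at 350 mg) is the true ratio. SAP Section 9.3.2 plans summaries and plots by treatment and no comparison with IV data. The expectation in Protocol Section 4.3 that SC exposure will be well below that at 7000 mg IV was written before this trial had data, and it uses no Cmax from this SAP.

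**The case for a change.** The strongest case for a change is that the text is plainly wrong, it concerns a primary endpoint, and correcting it costs one number. A final SAP should be usable as a check on output, and here correct output would appear to fail against the only worked conversion. Section 13.1 does not help, because reporting Cmax as received sits awkwardly with converting it from ng/mL to µg/mL.

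If the wrong factor did reach the report, absolute exposure would mislead. Suppose Cmax per mg were as high by the SC route as by IV, an upper-bound assumption. The true 1000 mg value would then be 1000 ÷ 7000 = 0.14 of the 7000 mg IV value. Inflated tenfold, it would appear as 1.43 times that value. If SC Cmax per mg were 30% to 50% of IV (an assumed range), it would appear as 0.43 to 0.71 times.

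What stands is that the printed number is wrong, it is not a reading artefact, and nothing elsewhere corrects it. What does not stand is the step from there to a wrong Cmax. That step needs someone to infer a false metric factor from a parenthetical illustration of rounding, against the units stated with it, and then to miss the conflict with the listed source data. The awkwardness with Section 13.1 is one of wording. Both passages exempt observed concentrations from rounding to three figures, and the Section 9.3.1 table settles the unit.

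**Conclusion.** The example is off by exactly a factor of 10, and that is certain. It is a clerical slip in a hypothetical value, not a defect in the analysis. The operative content is to keep the original digits and to report in µg/mL from ng/mL source data. It is complete without the example and gives 12.3456 µg/mL. No design figure, threshold or planned result depends on 123.456, no error in AUC is shown, and the between-cohort comparison would be unaffected even by a constant scaling error.

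This rests on two assumptions: that analysts convert by the stated units, and that ordinary checking compares Cmax with the listed concentrations. Both are routine. Tidying the decimal point if the SAP is reopened for another reason would be harmless, but the plan does not need to change on this account.

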#### Individual PK Parameter Rules

- Only quantifiable concentrations will be used to calculate PK Parameters with the exception of special handling of certain concentrations reported below the lower limit of quantification (BQL). Serum concentrations reported as BQL will be set to a value of zero when all of the following conditions are met:
  - The compound is non-endogenous.
  - The samples are from the initial dose period for a participant or from a subsequent dose period following a suitable wash-out period.
  - The time points occur before the first quantifiable concentration.
- All other BQL concentrations that do not meet the above criteria will be set to missing.
- Also, where two or more consecutive concentrations are BQL towards the end of a profile, the profile will be deemed to have terminated and therefore any further quantifiable concentrations will be set to missing for the calculation of the PK parameters unless it is considered to be a true characteristic of the profile of the drug.

#### Individual Concentration vs. Time Profiles

- Individual concentrations will be plotted utilizing actual sampling times.
- The terminal point selections will be indicated on a semi-logarithmic plot.

### Average Concentration vs. Time Profiles

- The average concentration profiles will be graphed using scheduled (nominal) sampling times.
- The average concentration profiles will be graphed using arithmetic average concentrations.
- The pre-dose average concentration for single-dose data from non-endogenous compounds will be set to zero. Otherwise, only quantifiable concentrations will be used to calculate average concentrations.
- Concentrations at a sampling time exceeding the sampling time window specified in the protocol, or  $\pm 10\%$ , will be excluded from the average concentration profiles.
- Concentrations excluded from the mean calculation will be documented in the final study report.
- A concentration average will be plotted for a given sampling time only if 2/3 of the individual data at the time point have quantifiable measurements that are within the sampling time window specified in the protocol or  $\pm 10\%$ . An average concentration estimated with less than 2/3 but more than 3 data points may be displayed on the mean concentration plot if determined to be appropriate and will be documented within the final study report.

### Treatment of Outliers during Pharmacokinetic Analysis

Application of this procedure to all PK analyses is not a requirement. Rather, this procedure provides justification for exclusion of data when scientifically appropriate. This procedure describes the methodology for identifying an individual value as an outlier for potential exclusion, but does not require that the value be excluded from analysis. The following methodology will not be used to exclude complete profiles from analysis.

#### Data within an Individual Profile

A value within an individual profile may be excluded from analysis if any of the following criteria are met:

- For PK profiles during multiple dosing, the concentration of the pre-dose sample exceeds all measured concentrations for that individual in the subsequent post-dose samples.
- For PK profiles during single dosing of non-endogenous compounds, the concentration in a pre-dose sample is quantifiable.
- For any questionable datum that does not satisfy the above criteria, the profile will be evaluated and results reported with and without the suspected datum.

### Data between Individual Profiles

1. If  $n < 6$ , then the dataset is too small to conduct a reliable range test. Data will be analyzed with and without the atypical value, and both sets of results will be reported.
2. If  $n \geq 6$ , then an objective outlier test will be used to compare the atypical value to other values included in that calculation:
  - a. Transform all values in the calculation to the logarithmic domain.
  - b. Find the most extreme value from the arithmetic mean of the log transformed values and exclude that value from the dataset.
  - c. Calculate the lower and upper bounds of the range defined by the arithmetic mean  $\pm 3 \times \text{SD}$  of the remaining log-transformed values.
  - d. If the extreme value is within the range of arithmetic mean  $\pm 3 \times \text{SD}$ , then it is not an outlier and will be retained in the dataset.
  - e. If the extreme value is outside the range of arithmetic mean  $\pm 3 \times \text{SD}$ , then it is an outlier and will be excluded from analysis.

If the remaining dataset contains another atypical datum suspected to be an outlier and  $n \geq 6$  following the exclusion, then repeat step 2 above. This evaluation may be repeated as many times as necessary, excluding only one suspected outlier in each iteration, until all data remaining in the dataset fall within the range of arithmetic mean  $\pm 3 \times \text{SD}$  of the log-transformed values.

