### Reporting of Excluded Values

Individual values excluded as outliers will be documented in the final report. Approval of the final report will connote approval of the exclusion.

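### The SAP's leave-one-out 3 SD outlier rule flags a valid value in up to 27–31% of clean cohorts of 6–7, its exclusion wording contradicts its own introduction, and parallel reporting stops at n = 6

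*SAP*

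**What the plan says.** SAP 9.3.1 handles atypical values between participants in two ways, according to n.

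- **n < 6:** the SAP says "then the dataset is too small to conduct a reliable range test". It then requires: "Data will be analyzed with and without the atypical value, and both sets of results will be reported".
- **n ≥ 6:** a range test on the log scale. Step 2b reads: "Find the most extreme value from the arithmetic mean of the log transformed values and exclude that value from the dataset". Steps 2c–2e form the mean ± 3 SD of the remaining values and, if the removed value lies outside, "then it is an outlier and will be excluded from analysis". A repeat is allowed if another value looks suspect and n is still at least 6.

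The introduction, Treatment of Outliers during Pharmacokinetic Analysis, says "Application of this procedure to all PK analyses is not a requirement" and that the method "does not require that the value be excluded from analysis".

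On disclosure, the SAP says "Individual values excluded as outliers will be documented in the final report". The General PK Parameter Rules add a table footnote for any AUC(0-∞) left out of the summaries. For AUCs and Cmax, SAP 9.1 states that "the geometric mean and geometric CV% will also be presented".

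**The concern.** There are three linked problems.

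1. The introduction leaves exclusion open, while step 2e orders it. Two analysts with the same data could report different primary summaries, and both could claim to have followed the SAP.
2. Three SD sounds strict but is not at this n. The SD comes from 5 or 6 values after the extreme one has been taken out, and it is then used to judge the largest of 6 or 7 deviations.
3. The SAP recognises that a range test is unreliable in small samples and asks for both sets of results there. It drops that safeguard at n = 6, where the test is hardly better than at n = 5.

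AUC(0-∞) and Cmax are the primary endpoints. Between-participant variability is a main product of a descriptive PK study of a new route, and removing valid extremes can only push the reported CV down.

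**Working it through.** **Inputs.** Active participants per cohort: 7 planned, at least 6 evaluable (SAP 5 and 7). PK is summarised by treatment (SAP 9.3.2), so n is one dose cohort. AUCs and Cmax are treated as log-normal (SAP 9.1). Between-participant CV is 40% (SAP 7), so the log SD is σ = √ln(1 + 0.40²) = √ln 1.16 = 0.385.

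**The plan's own figure.** The documents give no false-flag rate for the outlier rule. Their one computed figure is the chance of about 70% that a 90% CI lies within (0.7, 1.43) of the geometric mean at n = 6. As P[t(0.95, 5)·s/√6 ≤ ln(1/0.7)], with t(0.95, 5) = 2.015 and ln(1/0.7) = 0.357, it comes to 72.5% for σ = 0.385 and 68.1% for σ = 0.40. It reproduces, and it does not enter the argument below.

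**False-flag rate.** For any one clean value,

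(xᵢ − mean of the others) / (SD of the others × √(1 + 1/(n−1))) follows t with n − 2 degrees of freedom.

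A cut of 3 SD is therefore a t cut of 3/√(1 + 1/(n−1)). The value furthest from the overall mean also has the largest such ratio, and two values almost never exceed the cut together at these n. The rate per data set is then n times the two-sided tail probability.

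| n | t cut | tail probability per value | rate per data set |
|---|---|---|---|
| 5 | 2.68 | 0.0748 | 37% |
| 6 | 2.74 | 0.0520 | 31% |
| 7 | 2.78 | 0.0390 | 27% |
| 8 | 2.81 | 0.0309 | 25% |
| 9 | 2.83 | 0.0255 | 23% |

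Simulation of steps 2a–2e on clean data gives 31.2% at n = 6 and 27.3% at n = 7. The rate does not depend on the CV. For one parameter over two independent cohorts, the chance of at least one false flag is 1 − (1 − 0.312)² = 53% at n = 6, or 1 − (1 − 0.273)² = 47% at n = 7. Of the flagged values, 68% (n = 6) or 61% (n = 7) lie within 2 true SD of the true mean, and 97% or 95% within 3.

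**Effect on the summaries if every flag is acted on (simulation, true CV 40%).**

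| | n = 6 | n = 7, one pass |
|---|---|---|
| Average geometric CV | 38% → 33% | 39% → 34% |
| Mean log variance | 22% too low | 18% too low |
| Median CV in affected cohorts | 37% → 19% | 38% → 21% |

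The repeat cannot occur at n = 6, because 5 values then remain. It can occur once at n = 7, where it takes the average CV to 33%. The geometric mean is unbiased (ratio to truth 1.000), but the SD of its log rises from 0.157 to 0.175 at n = 6. If a 90% CI were computed, its coverage would be about 80% at n = 6.

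**Effect if only visibly atypical values are tested.** The SAP does not define atypical. As an illustrative assumption, suppose that the test is run only when a value is more than 2-, 2.5- or 3-fold from the geometric mean of the others. At n = 6 and CV 40% the false-flag rate is then 19%, 9% or 4%, and the average CV is 34.0%, 35.9% or 37.2%, against 38.4% with all values kept.

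**The case against.** The strongest reply is that 27–31% is a ceiling. The introduction makes the test optional and restricts exclusion to cases where it is scientifically appropriate, and step 2 starts from a value already thought atypical. The practical rate cannot be fixed from the documents. On this reading, step 2e only states the result once the team has chosen to apply the test. That stands as a limit on the size of the effect, and it is why the rates are given as upper bounds. It does not remove the conflict in wording, and undefined discretion over when to test is itself a reason to show both results.

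The SAP also discloses exclusions: in the final report, in a table footnote for AUC(0-∞) (that rule does not name Cmax), through N, and in listings. Complete profiles may not be removed by this route. A reader could recompute the full-data summary from 6 or 7 listed values. This too stands, but disclosure does not correct the CV printed in the table.

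Finally, no hypothesis test depends on this, the SAP lists no PK confidence interval, and the shift is small beside sampling noise: at n = 6 and true CV 40%, the full-data sample CV runs from 19% to 62% (5th to 95th percentile). Cohorts may also exceed 7 on active, where the ceiling is 25% (n = 8) or 23% (n = 9). These points keep the consequence moderate. They do not make a one-directional bias harmless.

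**Conclusion.** The concern holds. Step 2e contradicts the introduction to the procedure. As written, the test flags a valid value in up to 31% (n = 6) or 27% (n = 7) of clean cohorts, per parameter. The requirement to report both results ends at n = 6, although the false-flag rate has fallen only from 37% to 31%.

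The damage is to the reported geometric CV of the primary endpoints, at most about 5 percentage points on average at a true CV of 40%, and roughly a halving in the n = 6 cohorts affected. The rates assume log-normal data, as the SAP does, and that the test is run and acted on every time; selective use lowers them. This should be fixed, but it does not threaten any inferential conclusion.

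**What to change.** In SAP 9.3.1:

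1. Make the introduction and step 2e agree. Reword 2e so that a flagged value stays in the primary summaries of AUC(0-∞) and Cmax unless an assay, sampling or dosing cause is documented.
2. Apply the existing n < 6 rule at every n: analyse with and without the atypical value and report both.
3. State that the 3 SD test, including any repeat, is a flag only.

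Optionally, if a calibrated flag is wanted, a 5% false-flag rate per data set needs a multiplier of t(1 − 0.05/(2n), n − 2) × √(1 + 1/(n−1)). This is 4.85 × 1.095 = 5.3 SD at n = 6 and 4.38 × 1.080 = 4.7 SD at n = 7. The 5% target is a choice; the documents set none.

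The cost is SAP wording and one extra sensitivity table. Reported CVs may come out somewhat larger.
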